7.6 Safety Monitoring

A data safety monitoring board (DSMB) will be created to review the accruing data quarterly to:

- 1) Ensure that the study is adequately enrolling
- 2) Ensure data acquisition and protocol adherence rates are acceptable
- 3) Ensure that there are no serious safety concerns.

The DSMB will be assigned by NCCIH in coordination with the DCC. SAEs will be brought to the attention of the IRB and the DSMB in writing. As part of the Data Safety and Monitoring Plan (DSMP) we will perform continuous and interim analysis of accruing safety data. We have defined potentially treatment related SAEs (SAEs) that will be monitored throughout the course of the study.

The following guidelines will be used when considering halting the trial for safety: 1) $> 5\%$ of participants experience an unexpected, related, moderate or greater adverse event; 2) $\geq 2\%$ SAE overall that are unexpected and related to the intervention. The DSMB will consider this guidance when making recommendations regarding trial continuation.

8. INTERVENTION DISCONTINUATION

Criteria for Discontinuation

Participants will be discontinued from their assigned intervention if the study interventions become contraindicated, for example:

- A serious adverse event related to treatment occurs and thus makes it unsafe to continue with the assigned intervention.
- The participant has a specific cause of back pain and was erroneously diagnosed during screening.
- New evidence emerges and suggests it is unsafe for the participant to proceed with the intervention.

Due to the pragmatic nature of this study, interventions can be modified to accommodate patients and their needs (e.g., mobilization can be used in lieu of manipulation, or medication changes can be made in the medical care group to mitigate drug-induced side effects).

Criteria for discontinuation are met when the event is classified as serious and it is determined by the provider and/or the PI that it is unsafe to continue with the study intervention, or when a diagnosis for a specific cause of LBP is made.

Reasons for Discontinuation

All efforts will be taken to facilitate participant's completion of the study interventions. Potential reasons for early termination include:

- Participant develops a competing comorbid health condition that precludes adherence or makes it unsafe for them to proceed with their assigned treatment.
- A change in the participant's life (e.g., participant moves, dies, has other personal matters to attend).
- Participant chooses to discontinue on their own for any reason (e.g., participant is not responding to care or getting worse).
- Study closure by institute or oversight body.

With their permission, participants will continue to be followed if the study intervention is discontinued. Participants who have discontinued treatment will be asked to complete weekly and monthly self-report questionnaires (months 1-12), if possible. Efforts will be made to accommodate participant compliance (e.g., paper or electronic questionnaires, or data can be collected by phone).

If participants are unwilling to complete the entire self-report questionnaires during the follow-up phase, they will be asked to complete the primary outcome measures (e.g., pain intensity and frequency, low back disability) on a monthly basis. This can be further modified to include, at a minimum, measures at 2, 6 and 12 months.

Temporary Discontinuation of the Intervention

Potential reasons for temporary intervention discontinuation include:

- An acute health problem arises and prohibits their ability to attend the intervention (e.g., hospitalization). The length of discontinuation will be addressed on a case-by-case basis. All attempts will be made to minimize this discontinuation.
- Participant has a scheduled vacation. Participants will be asked to limit their vacation time to 1 week.

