6.2.4 Follow-up Visits

Intervention Visits

The following information will be collected at each intervention visit, which will occur as needed throughout the one year as there is no set schedule of treatments:

- Treatment delivery format – in-person, videoconference or phone
- Treatment administered – provider's record treatment administered including required, allowed and prohibited treatments to assess treatment fidelity and adherence. (Clinical notes will be documented in the medical record as required for patient management and for compliance with provider licensing requirements).
- Adverse events (AEs) - participants will be asked about the occurrence of AE/SAEs by their treatment provider at each visit. The AE protocol described in section 7, Safety and Assessments will be initiated and adhered to for all AEs identified.

Weekly Follow-up

Weekly outcomes will be collected electronically via direct patient self-report; participants who are unable to provide electronic data will be contacted directly by blinded study staff who will ascertain outcomes. Additional information related to data collection and quality assurance is described in section 10.

The following outcomes will be collected on a weekly basis for one year (\pm 2 days):

- Primary outcomes
 - Pain intensity
- Secondary outcomes
 - LBP frequency

Monthly Follow-up

Monthly follow-up data (Months 1-12) will be collected electronically via direct patient self-report. Participants who are unable to provide electronic data will be contacted directly by blinded study staff who will ascertain outcomes, or they will be mailed a paper copy of the questionnaire to complete and return to the study team. Additional information related to data collection and quality assurance is described in section 10.

The following outcomes will be collected on a monthly basis for one year (\pm 7 days):

- Primary outcomes
 - Disability - Roland Morris Disability Questionnaire
 - Low Back Pain Impact - subset of PROMIS-29
- Secondary outcomes
 - PROMIS measures, additional healthcare use, medication use, and productivity loss
 - AEs -participants will be queried about AEs associated with study interventions (e.g., increased pain, neurological symptoms, medication side effects etc.).^{11 142}
¹⁴³ The AE protocol described in section 7, Safety and Assessments will be initiated and adhered to for all AEs identified.

Week 2 Follow-up

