7.3 Adverse Events (AEs) and Serious Adverse Events (SAEs)

AE is generally defined as any unfavorable and unintended diagnosis, symptom, sign (including an abnormal laboratory finding), syndrome or disease which either occurs during the study, having been absent at baseline, or if present at baseline, appears to worsen. AEs are to be recorded regardless of their relationship to the study intervention.

The following scale will be used to grade AEs:

1. Mild: no intervention required; no impact on activities of daily living (ADL).
2. Moderate: minimal, local, or non-invasive intervention indicated; moderate impact on ADL.
3. Severe: significant symptoms requiring invasive intervention; subject seeks medical attention, needs major assistance with ADL.

We will measure and compare rates of AEs across the four treatment arms. We will specifically look for common treatment-related AEs that include: LBP, soreness at the treatment site, gastrointestinal symptoms, emotional discomfort, and other events. We will capture AEs prospectively from study participants through monthly surveys and at in-person/videoconference/telephone visits. Each unique occurrence will receive a separate ID in order to avoid duplication in documentation.

[figure not shown]
SAE is generally defined as any untoward medical occurrence that results in death, is life threatening, requires inpatient hospitalization or prolongation of existing hospitalization, results in persistent or significant disability/incapacity, or is a congenital anomaly or birth defect.

We will collect SAEs both passively through ad hoc reporting and through systematic evaluation at study visits. Given the nature of the interventions we do not anticipate any specific treatment-related SAEs and therefore focus on standard and LBP-specific serious events: death; severe or permanent disabilities; life-threatening conditions; hospitalizations; other important medical events; progressive neurological deficits, or cauda equina syndrome.

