7.5 Follow-up for Adverse Events

AEs/SAEs will be identified during the intervention phase at study visits and during the study follow-up phase using monthly self-report questionnaires (surveys) or through direct contact with study staff. Events will be followed until resolution or stabilization, whichever occurs first; resolution and stabilization will be determined by the PI with input from the study clinician when appropriate.

If an AE/SAE occurs during the intervention phase, the study clinician will monitor the AE/SAE while the participant is under their care, this will include a medical evaluation and treatment, or modifications to treatment as necessary to protect the participant and minimize harm. If warranted, referral to an outside provider will be made.

If an AE/SAE occurs during the follow-up phase, study staff will be in regular contact with the participant as the event permits.

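### Participants who stop treatment and decline the full questionnaires are no longer asked about adverse events, because the reduced follow-up in section 8 covers primary outcomes only

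*Combined protocol and SAP*

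**What the plan says.** Section 8 sets out follow-up after treatment stops in three steps.

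- **Default.** "Participants who have discontinued treatment will be asked to complete weekly and monthly self-report questionnaires (months 1-12), if possible". Paper, electronic and telephone options are offered.
- **Fallback.** "If participants are unwilling to complete the entire self-report questionnaires during the follow-up phase", then "they will be asked to complete the primary outcome measures (e.g., pain intensity and frequency, low back disability) on a monthly basis".
- **Minimum.** "This can be further modified to include, at a minimum, measures at 2, 6 and 12 months".

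The AE query sits elsewhere. Section 6.2.4 lists it among the monthly secondary outcomes, where "participants will be queried about AEs associated with study interventions". The schedule in section 6.1 places AEs at baseline, at intervention visits and in the monthly follow-up, with a footnote that participants may also report at any point. Section 7.5 says that events in the follow-up phase are found "during the study follow-up phase using monthly self-report questionnaires (surveys) or through direct contact with study staff".

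The data have a planned use. Section 7.3 states: "We will measure and compare rates of AEs across the four treatment arms". The secondary-outcomes paragraph of section 9 also includes AEs among the comparisons of each intervention group with medical care.

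**The concern.** When a participant will not complete the full questionnaires, the plan protects the primary outcomes and says nothing about safety. Two scheduled sources ask about AEs after baseline: the provider at treatment visits and the monthly survey. Stopping treatment removes the first, and the fallback removes the second. The trial then still contacts the person about pain and disability but has no stated duty to ask about harm.

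Section 7.1 has reportable events recorded until 7 days (non-serious) or 30 days (serious) after the last day of participation, and someone still supplying outcome data is still participating. At stake is whether AE rates mean the same thing for everyone in the four-arm comparison. Most participants would contribute solicited events. This subgroup would contribute only events that they volunteer or that staff happen to learn of.

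**Working it through.** The plan states no figure on this point. The check is a reading of the sections side by side, followed by counting.

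**1. Is the AE query a primary outcome measure?** Sections 1.1 and 3.2 name three primary outcomes: LBP Impact, average pain intensity and average disability. Section 6.2.4 puts AEs under secondary outcomes. A fallback limited to primary outcome measures therefore leaves the AE query out.

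**2. Scheduled survey AE queries.**
- Full follow-up: 12 months × 1 query = 12.
- Reduced set as written: 12 × 0 = 0.
- Stopping at the end of the 8-week treatment period: 12 − 2 = 10 queries remain under full follow-up (months 3–12) and 0 under the reduced set.

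**3. Outcome contacts that still occur.**
- Reduced set, monthly: 12 of 12.
- Reduced set, minimum: 3 of 12 = 25%.
- Stopping at the end of month 2: 10 contacts if monthly, 2 at the minimum (months 6 and 12). None carries a stated AE question.

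**4. What else could detect an event?**
- *Treatment visits (6.2.4, 7.1):* none after treatment stops.
- *Healthcare use, including emergency visits and hospitalizations (6.2.2, 6.2.4):* also a monthly secondary item, so it drops out as well.
- *Month 2 physical examination (6.1, 6.2.4):* its objective measures are secondary outcomes (6.2.2), and it is at most one contact.
- *Spontaneous reporting (6.1 footnote, 7.1, 7.3):* remains open.
- *Direct contact with staff (7.5):* remains, but nothing schedules it. The regular contact promised in 7.5 begins once an event has occurred, so it presupposes detection.
- *Events already known (7.1, 7.5):* followed until they resolve or stabilize.

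The change for this subgroup is from solicited to spontaneous or incidental ascertainment. It bears on later, second and non-serious events.

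**5. Effect of keeping one AE item at each reduced contact.**
- Minimum schedule: 3 queries instead of 0, with recall windows of 2 − 0 = 2, 6 − 2 = 4 and 12 − 6 = 6 months. Their sum, 2 + 4 + 6 = 12, covers the year.
- Monthly reduced schedule: 12 of 12 queries kept.

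**6. What cannot be computed.** The documents do not say how many participants are expected to stop treatment, how many of those would accept only the reduced set, or how many events they would have. The size of any undercount therefore cannot be derived. For scale, the halting guidance in section 7.6 at n = 1000 corresponds to more than 0.05 × 1000 = 50 participants for AEs of at least moderate grade and at least 0.02 × 1000 = 20 for SAEs, in both cases unexpected and related. Nothing in the documents shows how far an undercount would move either count.

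**The case against.** The strongest reply is that the fallback is a rescue for people who would otherwise give nothing, so the fair comparison is refusal and not full follow-up. By default the full questionnaires, with the AE query, continue after treatment stops. This stands. A reader might infer that safety data are lost for everyone who discontinues, and section 8 contradicts that.

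A reader might also infer that the loss falls on the people most likely to have been harmed, so that an arm with more harm-related stopping will show falsely low AE rates and mislead the DSMB. The documents do not carry this that far. One listed ground for stopping is "A serious adverse event related to treatment occurs and thus makes it unsafe to continue with the assigned intervention", but such an event is already known and is followed. Other listed reasons include moving and personal matters. Self-chosen stopping because of worsening is also listed, so a link with harm is possible, but nothing ties harm to refusing the questionnaires. The halting guidance counts only unexpected, related events, and some late harms one might think of, such as chemical dependence under medical care, are listed as expected in section 7.2.

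The arms also differ in expected visit numbers (section 5.4). That does not support an arm-specific loss here: visit queries end for anyone who stops attending, and section 8 does not govern them.

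Third, the reduced list is given as examples, and the examples are loose: they include pain frequency, which section 6.2.4 treats as secondary. Even so, they illustrate primary outcome measures, and loose wording gives staff no instruction to ask about AEs. The Data Safety Monitoring Plan is named as an appendix, but its text is not available here, so it may say more.

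Finally, 4- and 6-month recall is not equivalent to monthly queries. That stands, and it is why the fix includes a flag in the tables.

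**Conclusion.** The gap holds for one subgroup: participants who stop treatment and will not complete the full questionnaires. As section 8 is written, their scheduled survey AE queries fall to 0 while outcome contacts continue, monthly or at months 2, 6 and 12. Spontaneous reports and unscheduled staff contact are what remain, so some later, second or non-serious events may be under-recorded in the four-arm AE comparison.

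The conclusion assumes that the reduced set is applied as worded and that no unseen appendix adds an AE question. It does not establish that any arm will look safer than it is. This is a cheap improvement worth making, not a defect that undermines the safety monitoring as a whole.

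**What to change.** Add a sentence to section 8: every reduced contact, including the month 2, 6 and 12 minimum, keeps one AE/SAE item with a yes/no on hospitalization or emergency visits, covering the time since the last completed contact. Cross-refer to it from sections 6.2.4 and 7.5 so that the three sections agree. In the AE tables, flag participants followed on the reduced set, because their recall window can reach 6 months against 1 month for others.

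The cost is one or two items on a form used at contacts that already take place, plus the table flag. The downside is a slightly longer form for people who are already reluctant. If that is a worry, the AE item can follow the outcome items so that a refusal does not cost outcome data.

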9. STATISTICAL CONSIDERATIONS

Modifications to Statistical Analysis Plan Regarding the Sample Size and Power

(edited February 2023)

In consultation with NCCIH program staff and the DSMB in December 2022 we have modified the target enrollment to n=1000 participants (reduced from original n=1180). Our rationale for the modification is based on alignment with our updated primary outcome on chronicity. We have conducted extensive evaluation of power to detect meaningful effects using the LBP-Impact measure and our other primary outcomes. We have determined that it is appropriate to reduce the target sample size.

Modifications to Statistical Analysis Plan Regarding Primary Analysis and Treatment of Multiple Comparisons

(edited September 2022)

The trial initially had three main effectiveness objectives: (1) prevention of chronic LBP at twelve months; (2) recovery from acute/sub-acute LBP at six months; (3) Average of pain and disability over twelve months. In 2021, the NIH statistician overseeing the trial raised the question of the adequacy of the planned adjustment for multiplicity given the trial's three main effectiveness objectives and accompanying four primary outcome measures. In response to this concern, the lead investigators recommended the recovery objective be changed to a key secondary outcome. Early in the conduct of the trial it was decided and approved as a protocol change to include patients that had an acute aggravation of ongoing LBP, if the ongoing pain was not rated as severe in the month prior to the aggravation. This protocol change substantially lowers the proportion of patients that can be expected to recover according to our criteria (pain severity = 0 and RMD score ≤ 2). Given this change, the recovery outcome was less appropriate as a primary effectiveness objective and demoting it to a secondary outcome mitigates the concern of cross-objective control.

In consultation with NCCIH program staff and the DSMB in 2022 we have outlined our planned publications for presenting our main results and have revised the primary statistical test that would be used to evaluate differences in mean outcomes across the treatment groups. Specifically, rather than conduct individual tests of SMT alone, SSM alone, and the combination against medical care with adoption of a multiple comparisons correction for three tests we will now use an overall test of equality across the four groups to conduct a single omnibus hypothesis test followed by the estimation of key group comparisons using Fishers least significant difference methods to construct individual nominal 95% confidence intervals with reporting of the induced simultaneous coverage. These methods will be used for primary analysis of the 3 primary effectiveness outcomes : LBP-Impact and pain and disability.

We plan to present principal findings in two key publications. The first publication would focus on average pain and disability over 1-year as the multiple primary outcomes and present recovery at 6-months (previously a primary outcome) as one of the secondary outcomes. A second paper will focus on LBP Impact averaged over months 10-12 as the primary outcome .

Modifications to Statistical Analysis Plan Regarding Primary Outcome

(edited July 2021)

In consultation with the NCCIH program staff and DSMB in the Spring of 2021 we have changed our primary outcome for assessment of treatment impacts on chronicity prevention. Specifically, we have replaced our original NIH Task Force on Research Standards for Chronic LBP (referred to as RTF) dichotomous chronicity measure with the RTF quantitative impact measure. The LBP-Impact outcome measure is a subset of the Promise 29 measures, **which is already being collected at baseline and every month during the follow-up year from the start of the trial**. As a secondary outcome measure, we will compare differences across treatment groups in the distribution of patients with mild, moderate, and severe impact.

Modifications to Statistical Analysis Plan in Response to COVID-19 Impacts

(edited August 2020)

In Spring 2020 we suspended new enrollment into our study due to the COVID-19 pandemic. We continue to follow our participants and to maintain high-quality data collection. In order to resume trial enrollment, we are making adjustments to both care delivery and research data collection, and we have a modification to the enrollment and randomization that is responsive to risk mitigation. The key design and analysis modifications include:

- We will initially restart with restricted randomization to the MC and SSM groups. We will resume full factorial randomization once it is safe and appropriate. Specifically, in order to restrict physical interaction, we will conduct both remote assessment and intervention in a partial randomization period during which participants are randomized only to Medical Care (MC) or Supported Self-Management (SSM). Although we hope that partial randomization will only occur for the Fall of 2020, we recognize the need to be flexible by being able to consider reverting to restricted partial randomization during any future periods when physical contact is precluded. Since all possible randomization groups contribute to the ultimate effect estimates, the partial randomization period data is informative and can be combined with the pre-COVID data and the full factorial randomization data. In order to account for potential period-effects, we will modify all analyses to include adjustment for partial randomization time periods.
- Our statistical analysis will now adjust for study period (PERIOD) which is appropriate to account for our initial trial phase (UG3 and UH3 before March 2020), our restricted randomization phase, and resumption of full factorial randomization.
- Although we will ultimately have more subjects enrolled into the UMC and SSM groups due to restricted randomization we will not change our parameter of interest which is defined as the linear contrast capturing the equally weighted average of the SSM intervention effect combined from no-SMT and SMT strata, and similarly the equally weighted average of the SMT intervention effect combined from the no-SSM and SMM strata. (please see below for details)
- We have evaluated the impact on the power of our study subject to the potential for up to 240 subjects enrolled during restricted randomization. In our original protocol we focused sample size on obtaining adequate power for the Aim 1 chronicity endpoint assuming treatment relative risks of 0.70 (a 30% relative reduction), no interaction between treatments, and a control rate of 0.20. For this original scenario we used simulations to compute a power of 81% for either the overall SSM effect or the overall SMT effect. With partial randomization and an upper bound of n=240 subjects allocated during this period we obtain 78% power to detect an overall SSM effect and 77% power to detect an overall SMT effect. Therefore, the impact of altering the design to permit partial randomization is anticipated to have a minor reduction in power for our binary endpoints. In addition, the planned design will result in a minimum of n=30 per protocol pre-COVID subjects in the SMT and SSM+SMT groups combined with a full factorial randomization allocation of n=188 will permit a total of n=30+188=218 subject per group to evaluate mean differences in pain and disability scales across the four treatment groups. For MC and SSM groups we expect to have an upper bound of n=45 pre-COVID, n=120 partial randomization, and n=188 full factorial randomization subjects or n=45+120+188=354 total subjects per group. Our original balanced allocation would have produced n=1180/4= 295 subjects/group.

Statistical Analysis Plan

Introduction: A factorial trial is ideal when the two treatments under study are thought to act independently via different mechanisms.¹⁴⁶ Our interventions focus on a physical treatment approach (SMT) and a psychological intervention (SSM) for addressing acute LBP. A factorial design allows an efficient evaluation of each of these modalities using fewer subjects than would be required by separate trials. In addition, a crucial advantage of a factorial trial is the ability to evaluate whether the beneficial effects of each treatment modality combine in an additive, antagonistic, or synergistic fashion through evaluation of treatment interaction.¹⁴⁷

The trial was originally powered to detect meaningful differences in two dichotomous primary outcome measures, chronicity and recovery. These two outcomes are now secondary effectiveness measures.

Figure 9.1: The 2x2 factorial design (n=1000)

	SMT Intervention	No SMT Intervention
SSM Intervention	SMT + SSM Group A	SSM only Group B
No SSM Intervention	SMT only Group C	Usual Medical Care Group D

For the 3 quantitative primary outcomes collected longitudinally, RMDQ, Pain NRS and LBP-Impact we will conduct detailed analysis of the four groups formed by the factorial design since we have excellent power for such endpoints with our revised sample size of 1000 subjects. However, McAlister et al.¹⁴⁶ comment that “the most powerful analysis of a factorial trial is performed at the margins” and we adopt such an approach for our secondary binary chronicity and recovery outcomes. We explicitly define the separate treatment effects for SMT and SSM as the overall or average treatment effect that is obtained from pooling comparisons over strata defined by the other treatment approach (i.e., the SMT treatment effect obtained by pooling over strata

with and without SSM). In particular, we define the parameter of interest as a linear combination (contrast) of parameters from an appropriate regression model that acknowledges the potential for SMT and SSM interaction. Therefore, our proposed analyses for binary outcomes do not make any additive assumptions and is quite generally valid for creating meaningful overall effect summaries. Furthermore, by collecting detailed outcomes and health care utilization through one year we can conduct thorough mediation analyses and careful evaluation of concomitant treatment.

Our statistical analysis plan focuses on the effectiveness evaluation detailed under the Primary Objective in the protocol. We also provide a plan for mixed methods analyses (qualitative/quantitative) associated with the Secondary Objective: implementation.

Primary Effectiveness Outcome # 1: prevention of cLBP that is impactful at 10-12 months follow-up (LBP Impact scale (min 8 - max 50) using mean from months 10-12). The LBP impact scale includes measures of pain intensity, pain interference, and physical function from the PROMIS-29 Profile v2.0) we will determine the effectiveness of SMT, SSM, and the combination of SMT+SSM relative to medical care (MC)

LBP Impact Effectiveness Hypothesis: SMT alone will decrease the impact of low back pain with at least a moderate effect size of 0.3 standard deviations (Cohen's d). Similarly, SSM alone will decrease the impact of low back pain with at least a moderate effect size of 0.3 standard deviations. The combination SMT+SSM will lead to a stronger but not necessarily additive net reduction compared to the individual component interventions.

Design: As shown in Figure 9.1, we plan to enroll a total of 1000 subjects randomized to one of four treatment groups using a factorial design: medical care (MC); spinal manipulation therapy alone (SMT); supported self-management alone (SSM); and combined SMT+SSM.

LBP Impact Primary Analysis: Our primary analysis will compare each of the treatment groups to MC using an adjusted regression analysis. Specifically, Let Y_{ij} denote the primary outcome variable (average of LBP-Impact over months 10-12) for subject i in site j, and let $Site(2)$ be an indicator variable used to code the two recruitment sites. All analyses will adjust for site and the baseline risk status represented by $RiskGroup$ (0=medium risk; 1=high risk). In order to code the treatment groups we use the variables *SMT-Only* (0=no; 1=only spinal manipulation therapy), *SSM-Only* (0=no; 1=only supported self-management), and *SMT-and-SSM* (0=no, 1=both SMT and SSM). Given interruption by COVID-19 and an associated period of restricted randomization we will also adjust for this modified randomization using the variables *Period(k)* which will be an indicator for: 1=UG3 and UH3 through March 2020; 2=calendar period of restricted randomization; and 3=calendar period of resumed full factorial randomization. We will use an adjusted linear regression model with robust standard error to make inference regarding treatment groups using the following structure where X_{ij} denotes the covariates for subject i:

$$E(Y_{ij} | X_{ij}) = \beta_0 + \beta_1 \cdot Site(2)_j + \beta_2 \cdot RiskGroup_{ij} + \beta_3 \cdot SMT-Only_{ij} + \beta_4 \cdot SSM-Only_{ij} + \beta_5 \cdot SMT-and-SSM_{ij} + \beta_6 \cdot Period(2)_{ij} + \beta_7 \cdot Period(3)_{ij}$$

In the primary regression model the parameters of interest are:

β_3 = adjusted mean difference comparing SMT Only to UMC;

β_4 = adjusted mean difference comparing SSM Only to UMC;

β_5 = adjusted mean difference comparing combined SMT and SSM to UMC.

Our primary analysis will test the global hypothesis that these three treatment comparisons are all null using a multivariate Wald test with 3 degrees of freedom and alpha=0.05. We will then provide individual confidence intervals for each coefficient that compares an intervention group to medical care based on Fishers least significant difference methods which provide individual nominal 95% confidence intervals and also estimates the simultaneous coverage probability.

Power and Sample Size for Primary Outcome of LBP Impact: To characterize the power of our primary analysis (an overall F-test) we provide a summary table that considers potential standardized mean differences comparing the individual intervention arms to medical care. For a small effect size (Cohen's d of 0.2) and an additive effect we have greater than 90% power to reject the null. However, additivity may not hold so we also consider sub-additive scenarios, and the scenario where only one intervention is effective. For small to moderate effect sizes (0.2 – 0.3 standard deviations) we have >90% with our proposed design. We assume n=1000 enrolled with a realistic 90% follow-up that yields 900 evaluated subjects. We also account for the

imbalanced design due to restricted randomization that will yield approximately 300 subjects in the UMC and SSM alone groups and 200 subjects in each of the SMT and SMT+SSM groups. Power is calculated based on 5,000 simulation replications for each scenario and presented in Table 9.1.

The current design is robust to the enrollment target and follow-up assumptions. For example, with an enrollment of n=1000 subjects and 85% follow-up we would have 90% power for our expected alternative scenario with small treatment effects (0.30 standardized mean difference) that are not additive (sub-additive 1).

A secondary evaluation will consider whether the separate effects of SMT and SSM are potentially additive and this will be done using a formal test for interaction:

$$\text{Interaction Model: } E(Y_{ij} \mid X_{ij}) = \beta_0 + \beta_1 \cdot \text{Site}(2)_j + \beta_2 \cdot \text{RiskGroup}_{ij} + \beta_3 \cdot \text{SMT}_{ij} + \beta_4 \cdot \text{SSM}_{ij} + \beta_5 \cdot \text{SMT}_{ij} \cdot \text{SSM}_{ij} + \beta_6 \cdot \text{Period}(2)_{ij} + \beta_7 \cdot \text{Period}(3)_{ij}$$

Table 9.1: Chronicity based on LBP-Impact averaged over months 10-12 of follow-up. Power for the overall F-test of equality of means under various alternative scenarios. (alpha = 0.05)

Alternative	SMT Alone	SSM Alone	SMT + SSM	Power
Additive	0.20	0.20	0.40	93%
Sub-Additive 1	0.25	0.25	0.35	91%
Sub-Additive 2	0.30	0.30	0.30	94%
Sub-Additive 3	0.25	0.25	0.25	81%
Single effect 1a	0	0.30	0.30	98%
Single effect 1b	0.30	0	0.30	94%
Single effect 2a	0	0.25	0.25	91%
Single effect 2b	0.25	0	0.25	80%

In this model a test of $H_0: \beta_5=0$ allows us to determine if there is strong evidence for synergistic or antagonistic effects associated with combined treatment.

Secondary Effectiveness Outcome of Chronicity: Chronic back pain: For a subject to be classified as a chronic back pain patient at the 1-year assessment they must endorse having “a back pain problem that has persisted at least 3 months and has resulted in pain on at least half of the days in the past 6 months”. This outcome is based on specific items

from the NIH Research Task Force recommended minimal data set:⁷³ Question 1 on LBP duration; and Question 2 on the proportion of days that LBP has been a problem in the past 6 months. To evaluate chronic back pain we will consider the 1-year status as a key secondary outcome for chronicity prevention, and will use the 6-month status as another key secondary outcome.

Chronicity Hypothesis: SMT alone will decrease the rate of cLBP by 6-9% from a baseline MC level anticipated to be 20% or higher. Similarly, SSM alone will decrease the rate of cLBP by 6-9%, and the combination of SMT+SSM will lead to an additive net reduction.

Secondary Chronicity outcome Analysis: The analysis of the secondary binary outcome will use parallel marginalized tests of the average SMT treatment effect and the average SSM treatment

effect using linear contrasts from a logistic regression model. Specifically, we will use two separate Wald tests based on logistic regression, with stratification by recruitment site and baseline risk group (medium, high). Let Y_{ij} denote the primary outcome status (0=not chronic; 1=chronic) for subject i in site j , and let $Site(2)$ be an indicator variable used to code the two recruitment sites. All analyses will adjust for site and the baseline risk status represented by $RiskGroup$ (0=medium risk; 1=high risk). In order to code the treatment groups we use the variables SMT (0=no; 1=spinal manipulation therapy), and SSM (0=no; 1=supported self-management). Given interruption by COVID-19 and period of restricted randomization we will adjust for this using the variables $Period(k)$ which will be an indicator for: 1=UG3 and UH3 through March 2020; 2=calendar period of restricted randomization; and 3=calendar period of resumed full factorial randomization. Regression models for the outcome are used to structure the probability of chronic back pain as follows:

$$Additive\ Model \quad \text{logit}[P(Y_{ij} = 1 | X_{ij})] = \beta_0 + \beta_1 \cdot Site(2)_j + \beta_2 \cdot RiskGroup_{ij} + \beta_3 \cdot SMT_{ij} + \beta_4 \cdot SSM_{ij} + \beta_5 \cdot Period(2)_{ij} + \beta_6 \cdot Period(3)_{ij}$$

$$Full\ Model \quad \text{logit}[P(Y_{ij} = 1)] = \beta_0 + \beta_1 \cdot Site(2)_j + \beta_2 \cdot RiskGroup_{ij} + \beta_3 \cdot SMT_{ij} + \beta_4 \cdot SSM_{ij} + \beta_5 \cdot SSM_{ij} \cdot SMT_{ij} + \beta_6 \cdot Period(2)_{ij} + \beta_7 \cdot Period(3)_{ij}$$

Our original application proposed using an additive model to generate a single summary parameter that describes the SMT effect (β_3) and the independent SSM effect (β_4). However, the additive model uses an assumption that the effect of one intervention is independent of whether the other intervention is delivered. Such an assumption is not necessary, and a full model can be used to make inference on a single linear contrast for each treatment that represents an average treatment effect.

The “Full Model” can then be used to derive an overall or average effect of SMT, and an overall or average effect of SSM. Specifically, focusing on the effect of SMT the model yields:

$$\begin{aligned} \text{SMT effect when SSM=0:} & \quad \beta_3 \\ \text{SMT effect when SSM=1:} & \quad \beta_3 + \beta_5 \\ \text{Average SMT effect:} & \quad \frac{1}{2} \beta_3 + \frac{1}{2} (\beta_3 + \beta_5) = \beta_3 + \frac{1}{2} \beta_5 \end{aligned}$$

Our original analysis plan used an additive regression model that did not include the interaction term in order to generate a model-based average effect of SMT. By using the full model, we are not making any assumption of constancy of SMT effect across the two strata defined by SSM, and are directly calculating the average of the two treatment effects as the linear contrast that will be used to summarize the overall effect of SMT. The model can similarly be used to derive a linear contrast that represents the average SSM effect:

$$\begin{aligned} \text{SSM effect when SMT=0:} & \quad \beta_4 \\ \text{SSM effect when SMT=1:} & \quad \beta_4 + \beta_5 \\ \text{Average SSM effect:} & \quad \frac{1}{2} \beta_4 + \frac{1}{2} (\beta_4 + \beta_5) = \beta_4 + \frac{1}{2} \beta_5 \end{aligned}$$

